5.2 Administration and Monitoring

Three disease groups will be studied.

Group A: Patients with locally advanced or metastatic adenocarcinoma who are responding (defined as stable disease or tumor volume reduction) following 3 cycles of first line chemotherapy will be evaluated in the clinic and receive 6 infusions with a fixed dose of multiTAA T cells starting on chemotherapy cycle 4 and occurring on the 4th week of the cycle, which is a chemotherapy “off” week.

Group B: Patients with locally advanced or metastatic adenocarcinoma who have failed first line chemotherapy or are intolerant or ineligible to receive standard of care chemotherapy will be evaluated in the clinic and receive 6 infusions (administered at monthly intervals) with a fixed dose of multiTAA T cells.

Group C: Patients with resectable pancreatic adenocarcinoma following completion of neoadjuvant chemotherapy, radiotherapy or combination. These patients will receive 6 infusions with a fixed dose of multiTAA T cells. One infusion will occur 4 weeks prior to surgical resection (with an option to infuse up to one week earlier) and after the completion of all pre-operative chemotherapy and/or radiation. The subsequent 5 infusions will occur at monthly intervals beginning 8 weeks post-surgery.

Monitoring: Patients will be monitored for clinical toxicity by the CTEP NCI Common Toxicity Criteria Scale (Version 4.X, See Section 12.3) with the exception of CRS toxicities that are related to T cell infusions. CRS toxicities will be graded according to Appendix I. We will also analyze immunological parameters including T cell frequencies by ELIspot and multimer studies in patients who have HLA types for which multimers are available. Functional analyses (antigen-specific cytotoxicity and cytokine release) will be performed by chromium release assays and ELIspot/intracellular cytokine staining, respectively. The levels of serum cytokines before and following infusion will be compared. A time period of 4 weeks post the 1st infusion will constitute the time for clinical efficacy and safety monitoring. Thereafter patients will receive 5 additional infusions of cells at the same cell dose (or below the patient's original dose can be administered) at monthly intervals. Patients that undergo surgical resections (Group C) will receive 1 infusion prior to surgery and 5 additional infusions of cells at the same cell dose (or below the patient's original dose can be administered) at monthly intervals after surgery.

6.0 TREATMENT PLAN

This study will evaluate the clinical safety and look for evidence of benefit associated with the administration of tumor-targeted T cells in a fixed dose study.

6.1 Dosage

Patients will receive 6 infusions of multiTAA T cells at a fixed dose of 1×10^7 cells/m².

6.2 Dose Schedule

This protocol is designed as a pilot fixed-dose study.

Each patient will receive 6 infusions of multiTAA T cells at a fixed cell dose (1×10^7 cells/m²) within the same week at the times specified in the study calendar. The expected volume of infusion will be 1 to 10 cc.

- 6.3 Patients may be premedicated with diphenhydramine (Benadryl) up to 1mg/kg IV (max 50mg) and acetaminophen (Tylenol) 10mg/kg po (max 650mg), though this is not mandatory.
- 6.4 Cell Administration: Tumor-specific T cells will be given by intravenous injection over 1-10 minutes through either a peripheral or a central line.
- 6.5 Monitoring will be undertaken according to institutional standards for administration of blood products with the exception that the injection will be given by a physician.
- 6.6 Patients will receive supportive care for acute or chronic toxicity, including blood components or antibiotics, and other intervention as appropriate.
- 6.7 All treatments will be administered at the Center for Cell and Gene Therapy in Houston Methodist Hospital. Patient follow up and regular care will be at the Dan L. Duncan Cancer Center at Baylor Clinic or Smith Clinic.

7.0 PATIENT EVALUATION

7.1 Follow-up Interval

Patients shall be seen in clinic prior to each T cell infusion and evaluated (seen in clinic or contacted by research coordinator) at 1 and 2 weeks after each infusion, week 4, 6, and 8 after the last infusion and then at 3, 6, 9 and 12 months after the last infusion. Study-related blood draws will cease 12 months after the last T cell infusion but we will then continue to follow patients clinically for up to 4 additional years (total of 5 years follow-up) to evaluate long-term disease responses. If persistence of cells is noted at the 12 month visit, additional follow up will be added. Additional visits will be obtained as clinically indicated.

- 7.2 A complete history and physical examination is necessary prior to administration of multiTAA T cells. Medical history will be obtained at every follow-up visit and will be reviewed annually for 5 years.

7.3 Other Studies

- 7.3.1 The following investigations will be obtained at the time points specified in the study calendar:
CBC and differential, BUN, creatinine, bilirubin, SGOT, SGPT, alkaline phosphatase, Na, K, Cl, CO₂, albumin and total protein, and CA19-9.
- 7.3.2 Pregnancy testing (blood) is required on female patients of childbearing potential prior to multiTAA T cell infusion #1.
- 7.3.3 Diagnostic imaging (CT scans, MRI, nuclear imaging) and/or blood tests (serum cytokines) to document measurable disease and response to therapy prior to the first infusion and every 2-3 months thereafter for up to 1 year after the last infusion, as per standard clinical care monitoring for patients with pancreatic cancer. The time may vary by 1-2 weeks due to scheduling issues and may be done earlier if clinically indicated. If diagnostic imaging studies are performed at other times either during or after treatment on this study, that data will be collected and information gained will be used for this study.
- 7.3.4 The following investigations will be obtained at the time points specified in the study calendar. 20-40ml of peripheral blood will be collected in preservative-free heparin.. This blood will be used for analysis of specificity of multiTAA T cell response using HLA multimer analysis and immune function assays including ELIspot, intracellular cytokine staining and cytotoxicity assays. Serum will be batched for analysis of blood cytokine levels. These studies will be done on patients on whom the appropriate reagents are available.
- 7.3.5 Study specific blood tests will cease 12 months after the last T cell infusion but we will continue to follow patients clinically once a year for up to 4 additional years (total of 5 years follow-up) to evaluate long term disease responses.
- 7.3.6 Other Tissues: Should the patient undergo a tumor biopsy/surgical resection at any time while they are on study, a sample of this will be used to assess the tumor antigen expression profile and to look for evidence of T cell infiltration.
- 7.3.7 If a patients' hemoglobin is <7.0g/dl at any of the evaluation times, the amount of blood drawn for the evaluation will be reduced and may be obtained over more than one venipuncture, if necessary.

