- 4.3.12 Due to unknown effects of this therapy on a fetus, pregnant women are excluded from this research. The male partner should use a condom. Females of child-bearing potential must be willing to utilize one of the more effective birth control methods during the study unless female has had a hysterectomy or tubal ligation.

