10.0 MODIFIED FOLLOW-UP AND OFF STUDY CRITERIA

10.1 Criteria for Modified Follow-Up

The following criteria will result in the patient being ineligible for further treatment on the protocol, although response data will continue to be collected as applicable.

10.1.1 Any patient who develops grade III-IV toxicity related to multiTAA T cells . In such patient the toxicities will be followed until resolution or until their off study date. Although no toxicity has been associated with the infusion of this product in patients with Hodgkin and non-Hodgkin lymphoma or multiple myeloma, we will actively look for evidence of any adverse events, such as cytokine release syndrome.

10.1.2 Any patient who receives any other hematopoietic cell product excluding blood or platelets. In such patients, adverse event data collection will cease.

- 10.1.3 Any patient who experiences Grade 3 or 4 cytokine release syndrome that persists beyond 72 hours. In such patients, the toxicity will be followed until resolution or until their off study date.
- 10.1.4 Any patient whose disease progresses (based on RECIST criteria) and who receives another therapy. In such patients, adverse event data collection will cease.
- 10.1.5 If the patient desires to discontinue treatment or if the physician feels that it is in the best interest of the patient.

Patients who meet modified follow-up criteria remain on long-term follow-up as per the Summary of Monitoring (see table in Section 7.3.1)

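### Pregnancy is tested once, before infusion 1, although the reason for excluding it applies equally to the five later infusions; retesting before each infusion is a cheap, low-severity improvement

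*Combined protocol and SAP*

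**What the plan says.** On testing, Section 7.3.2 reads: "Pregnancy testing (blood) is required on female patients of childbearing potential prior to multiTAA T cell infusion #1". The pregnancy rows of the Section 7.4 calendars refer back to 7.3.2, and no column after the pre-infusion one carries a mark. The Group A row appears empty in the available text. That may be a text-extraction effect, and nothing here relies on it.

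On the reason for the exclusion, Section 4.3.12 says: "Due to unknown effects of this therapy on a fetus, pregnant women are excluded from this research". Section 4.4.3 also lists pregnancy as a treatment exclusion.

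The protocol has these safeguards:
- Contraception during the study (4.3.12): "The male partner should use a condom. Females of child-bearing potential must be willing to utilize one of the more effective birth control methods".
- A visit before every dose (7.1): "Patients shall be seen in clinic prior to each T cell infusion". Patients are also to be "evaluated (seen in clinic or contacted by research coordinator) at 1 and 2 weeks after each infusion".
- History (7.2): "Medical history will be obtained at every follow-up visit".
- A discretionary end to treatment (10.1.5), which applies "if the physician feels that it is in the best interest of the patient".

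Section 10.1 introduces its list with "The following criteria will result in the patient being ineligible for further treatment on the protocol". The list covers related toxicity, another cell product, persistent severe CRS, progression with another therapy, and patient or physician decision. It does not name pregnancy.

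**The concern.** Pregnancy status can change during treatment, so one negative result says little about a dose given months later. The protocol's stated reason for caution is that the effect on a fetus is unknown, and this is as true of infusion 6 as of infusion 1. The listed safeguards either lower the chance of conception or depend on the patient knowing or suspecting that she is pregnant. A woman who conceives after the single test and does not yet know it could therefore receive one or more further infusions. The harm is improbable, but it could be irreversible and would fall on a third party.

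**Working it through.** The plan gives no figure on this point to reproduce. The check is schedule arithmetic, followed by an order-of-magnitude estimate on labelled assumptions.

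**Inputs from the protocol.** Six infusions are planned (6.1). Group A is infused once per four-week chemotherapy cycle and Group B monthly (5.2). Group C receives infusion 1 four weeks before surgery, or up to one week earlier, infusion 2 eight weeks after surgery, and the rest monthly (5.2 and the 7.4 footnotes). Each group has at most 15 patients, 45 in total (9.1).

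**Infusions without a scheduled test.** 6 - 1 = 5 of 6.

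**Time from first to last infusion.**
- Groups A and B: weeks 0, 4, 8, 12, 16, 20, so 20 weeks. For Group B this follows the monthly interval in 5.2, because the calendar marks look shifted in the available text.
- Group C, infusion 1 to 2: 4 + 8 = 12 to 5 + 8 = 13 weeks.
- Group C, infusion 2 to 6: 4 intervals x 4 weeks = 16 weeks. The calendar mark reads as week 15, but week 16 fits a calendar that ends at week 18, two weeks after the last infusion.
- Group C in total: 12 + 16 = 28 to 13 + 16 = 29 weeks.
- With calendar months in place of four-week intervals, the totals are about 21.7 weeks (A, B) and 29.4-30.4 weeks (C).

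**Group C gap under 7.1.** The last contact set by 7.1 after infusion 1 is at week 2. The next is the visit before infusion 2, so the interval is 12 - 2 = 10 to 13 - 2 = 11 weeks. Surgery falls inside it. Imaging every 2-3 months (7.3.3 and 8.0) may also fall inside it. The protocol specifies no pregnancy test at either.

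**Infusions spanned by an unrecognised pregnancy.** At four-week spacing, an assumed unrecognised period of 4 weeks covers 4/4 = 1 infusion, and one of 8 weeks covers 8/4 = 2.

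**Expected pregnancies.** The documents do not give the number of women of childbearing potential or a pregnancy rate. Assumed: 5-20% of patients (0.75-3 per group of 15, or 2.25-9 in all), everyone receives six infusions, and 1-5% conceive per year under the required contraception.
- Low end: 0.75 x (20 + 20 + 28)/52 = 0.98 woman-years; x 0.01 = 0.01.
- High end: 3 x (20 + 20 + 29)/52 = 3.98 woman-years; x 0.05 = 0.20.

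**Added assays.** 2.25 x 5 = about 11, to 9 x 5 = 45, in the whole trial.

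**The case against.** The strongest reply is that this is a deliberate and coherent choice. Section 7.3.2 is explicit, the Group B and C calendars agree with it, and nothing in the documents requires retesting. Contraception with a partner condom, a clinic visit before each dose and repeated history form a lighter but sensible strategy. The estimate above also leans high. It assumes that all patients complete six infusions, whereas 9.2 and 10.1 provide for patients who do not, and it counts every pregnancy, not only those still unrecognised at the next dose. All of this stands. It limits severity, but it does not supply a means of detecting an early pregnancy.

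A reader might draw two stronger inferences that the documents do not support.

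The first is that the silence of 10.1 leaves a woman known to be pregnant eligible for further cells. The statement in 4.3.12 excludes pregnant women from the research as a whole, and 10.1.5 lets the physician end treatment. A known pregnancy is therefore already covered, and naming it in 10.1 would only make the text clearer.

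The second is that Group C patients go unobserved for 10-11 weeks. That interval describes the contacts in 7.1 only. Surgery takes place within it, imaging may, and 7.1 allows additional visits when clinically indicated. What is absent is a specified pregnancy test, not contact with the patient.

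**Conclusion.** The point holds as a low-severity improvement to participant safety. The single test is firm on the text, and so is the schedule arithmetic. The size is not: the 0.01-0.20 rests wholly on assumed inputs and should be read as a ceiling of that order on exposed pregnancies, not as an estimate of them. It would be wrong to call this an error in the plan or a statistical defect, since no sample size, error rate or endpoint depends on it. The conclusion concerns the protocol text only. The consent pages and the site's operating procedures were not available and may add testing.

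**What to change.** In 7.3.2, change the timing from infusion 1 only to 'prior to each multiTAA T cell infusion', and state that the result must be known before the cells are given. Mark the test at each infusion visit in the three group calendars. Optionally, for clarity, add a line to 10.1 naming pregnancy as a reason to end treatment.

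The cost is wording edits and at most five extra assays per woman of childbearing potential, largely on blood already drawn around infusion visits, with no new visits planned. The real burden is timing: the site needs a same-day result or a draw shortly before. Because infusions are given at one hospital and regular care takes place at separate clinics (6.7), this may need coordination between sites.

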7.4 Summary of Monitoring

Group A Study week	Pre- Infusion	Treatment	Wk1	Wk2	Wk3	Wk4	Wk5	Wk6	Wk7	Wk8	Wk9	Wk10	Wk11
Events			SOC	SOC	SOC		SOC	SOC	SOC		SOC	SOC	SOC
T cells		x				x				x			
History	X		x	x		x	x	x	x	x	x	x	
Physical	X					x				x			
CBC/diff	X					x				x			
BUN, creatinine, bilirubin, SGOT, SGPT, alkaline phosphatase, Na, K, Cl, CO ₂ , albumin, total protein, CA 19-9 ^s	X					x				x			
Imaging [^]	X												
Immune Function [↓]	X		x	x		x	x	x		x	x	x	
Pregnancy test [#]													

Group A Study week	Wk12	Wk13	Wk14	Wk15	Wk16	Wk17	Wk18	Wk19	Wk20	Wk21	Wk22*
Events		SOC	SOC	SOC		SOC	SOC	SOC		SOC	SOC
T cells	x				x				x		
History	x	x	x		x	x	x		x	x	x
Physical	x				x				x		
CBC/diff	x				x				x		
BUN, creatinine, bilirubin, SGOT, SGPT, alkaline phosphatase, Na, K, Cl, CO ₂ , albumin, total protein, CA 19-9 ^s	x				x				x		
Imaging [^]											
Immune Function [↓]	x	x	x		x	x	x		x	x	x
Pregnancy test [#]											

Group B Study week	Pre- Infusio n	Treatment	Wk 1	Wk2	Wk3	Wk4	Wk5	Wk6	Wk7	Wk8	Wk9	Wk10	Wk11
T cells		x			x				x				
History	x		x	x		x	x	x	x	x	x	x	
Physical	x					x			x				
CBC/diff	x					x			x				
BUN, creatinine, bilirubin, SGOT, SGPT, alkaline phosphatase, Na, K, Cl, CO ₂ , albumin, total protein, CA 19-9 ^s	x					x			x				
Imaging [^]	x												
Immune Function ⁺	x		x	x		x	x	x	x	x	x	x	
Pregnancy test [#]	x												

Group B Study week	Wk12	Wk13	Wk14	Wk15	Wk16	Wk17	Wk18	Wk19	Wk20	Wk21	Wk22*
T cells	x				x				x		
History	x	x	x		x	x	x	x	x	x	x
Physical	x				x			x			
CBC/diff	x				x			x			
BUN, creatinine, bilirubin, SGOT, SGPT, alkaline phosphatase, Na, K, Cl, CO ₂ , albumin, total protein, CA 19-9 ^s	x				x			x			
Imaging [^]											
Immune Function ⁺	x	x	x		x	x	x		x	x	x
Pregnancy test [#]											

Group C Study week	Pre- Infusio n	Treatm ent [§]	Wk1	Wk 2	Wk 3	Wk4	Infusi on #2 [%]	Wk1	Wk 2	Wk 3	Wk 4	Wk 5	Wk 6	Wk 7
Events						Surgery		SO C	SO C	SO C		SO C	SO C	SO C
T cells		x					x				x			
History	x		x	x			x	x	x		x	x	x	
Physical	x						x				x			
CBC/diff	x						x				x			
BUN, creatinine, bilirubin, SGOT, SGPT, alkaline phosphatase, Na, K, Cl, CO ₂ , albumin, total protein, CA 19-9 [§]	x						x				x			
Imaging [^]	x													
Immune Function [⊥]	x		x	x			x	x	x		x	x	x	
Pregnancy test [#]	x													

Group C Study week	Wk8	Wk9	Wk10	Wk11	Wk12	Wk13	Wk14	Wk15	Wk16	Wk17	Wk18*
Events		SOC	SOC	SOC							
T cells	x				x			x			
History	x	x	x		x	x	x	x	x	x	
Physical	x				x			x			
CBC/diff	x				x			x			
BUN, creatinine, bilirubin, SGOT, SGPT, alkaline phosphatase, Na, K, Cl, CO ₂ , albumin, total protein, CA 19-9 [§]	x				x			x			
Imaging [^]											
Immune Function [⊥]	x	x	x		x	x	x		x	x	x
Pregnancy test [#]											

Generic Long term follow-up Table

Study timepoint (after last infusion)	Wk4	Wk6	Wk8	Mth 3, 6, 9, 12	Yr 2, 3, 4, 5
T cells					
History	x	x	x	x	x
Physical					
CBC/diff					
BUN, creatinine, bilirubin, SGOT, SGPT, alkaline phosphatase, Na, K, Cl, CO ₂ , albumin, total protein, CA 19-9 [§]					
Imaging [^]					
Immune Function [⊥]	x	x	x	x	
Pregnancy test [#]					

SOC = Standard of care

* Following this study time point monitoring will be performed per long term follow-up Table & For Group C the 1st infusion occurs at 4 weeks prior to surgery with a provision to infuse up to 1 week earlier to allow for variations in surgery scheduling.

% For Group C the 2nd infusion will occur 8 weeks post-surgery

[^]See Section 7.3.3. Imaging studies can be performed within 8 weeks of T cell administration and post-infusion monitoring will be per standard of care

[⊥] See Section 7.3.4

[#] See Section 7.3.2

\$ Or any other serum tumor marker that is elevated because of the pancreatic tumor (such as CEA or CA-125)

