4.0 PATIENT ELIGIBILITY

4.1 Procurement Inclusion Criteria

4.1.1 Any patient with biopsy proven pancreatic adenocarcinoma.

4.1.2 Patients with life expectancy \geq 6 months.

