4.3.3 Patients with life expectancy ≥ 12 weeks

4.3.4 Age ≥ 18

4.3.5 Pulse oximetry of $>95\%$ on room air in patients who previously received radiation therapy

4.3.6 Patients with an ECOG score of ≤ 2 or Karnofsky score of ≥ 50 as described below:

ECOG Performance Status	
Grade	ECOG
0	Full active, able to carry on all pre-disease performance without restriction
1	Restricted in physically strenuous activity but ambulatory and able to carry out work of a light or sedentary nature, e.g., light house work, office work
2	Ambulatory and capable of all selfcare but unable to carry out any work activities. Up and more than 50% of waking hours
3	Capable of only limited selfcare, confined to bed or chair more than 50% of waking hours
4	Completely disabled. Cannot carry on any selfcare. Totally confined to bed or chair
5	Dead

Performance Status Criteria	
Karnofsky performance scores are intended to be multiples of 10	
Karnofsky	Description
Score	Description
100	Normal, no complaints, no evidence of disease

90	Able to carry on normal activity, minor signs or symptoms of disease
80	Normal activity with effort; some signs or symptoms of disease.
70	Cares for self, unable to carry on normal activity or do active work.
60	Required occasional assistance, but is able to care for most of his/her needs.
50	Requires considerable assistance and frequent medical care.
40	Disabled, requires special care and assistance.
30	Severely disabled, hospitalization indicated. Death not imminent.
20	Very sick, hospitalization indicated. Death not imminent.
10	Moribund, fatal processes progressing rapidly.

- 4.3.7 Patients with bilirubin $\leq 2x$ upper limit of normal, AST $\leq 3x$ upper limit of normal, Hgb ≥ 7.0 g/dl (transfusion allowed).
- 4.3.8 Patients with a creatinine $\leq 2x$ upper limit of normal for age
- 4.3.9 Patients should have been off other investigational therapy for one month prior to receiving treatment on this study.
- 4.3.10 For Groups B or C patients must be off conventional therapy for at least 1 week prior to receiving treatment on this study.
- 4.3.11 Informed Consent explained to, understood by and signed by patient. Patient given copy of informed consent.

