8.0 RESPONSE CRITERIA

A 4-week period after the first infusion will constitute a course, which will be evaluated for critical toxicity.

Patients with measurable disease will be assessed by standard criteria to determine clinical response. Evaluations of tumor size will be performed pre-infusion and approx. every 2-3 months thereafter as per standard clinical care patient monitoring. All patients who receive multiTAA T cells and continue to be enrolled on the study will be evaluable for response. Patient long term overall and progression free survival will also be evaluated at 1 year and then annually for up to an additional 4 years (total of 5 years follow-up).

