8.1 Definitions

This study will use the RECIST 1.1 criteria

Definitions

Response and progression will be evaluated in this study using the international criteria proposed by the Response Evaluation Criteria in Solid Tumors (RECIST 1.1) Committee. Changes in only the largest diameter (unidimensional measurement) of the tumor lesions are used in the RECIST criteria. Measurable lesions are defined as those that can be accurately measured in at least one dimension (longest diameter to be recorded) as >10 mm with CT scan, MRI, or clinically using calipers. The investigator will identify up to 5 measurable lesions to be followed for response. Serial measurements are to be done with CT or MRI. The same method of assessment is to be used to characterize each identified and reported lesion at baseline and during follow-up.

Complete Response: Disappearance of all target lesions

Partial Response (PR): At least a 30% decrease in the sum of the longest diameter (LD) of target lesions, taking as reference the baseline sum LD

Progressive Disease (PD): At least a 20% increase in the sum of the LD of target lesions, taking as reference the smallest sum LD recorded since the treatment started or the appearance of one or more new lesions

Stable Disease (SD): Neither sufficient shrinkage to qualify for PR nor sufficient increase to qualify for PD, taking as reference the smallest sum LD since the treatment started

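### Groups B and C: the baseline scan may be 8 weeks old and may precede the last conventional therapy, so change before infusion 1 can be scored as response (Group B) or new-lesion progression after T cells

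*Combined protocol and SAP*

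**What the plan says.** - **Age of the scan.** The 7.4 footnote says "Imaging studies can be performed within 8 weeks of T cell administration". Section 7.3.3 requires imaging before the first infusion, and 8.0 says "Evaluations of tumor size will be performed pre-infusion and approx. every 2-3 months thereafter".
- **Washout.** Section 4.3.10 says "For Groups B or C patients must be off conventional therapy for at least 1 week prior to receiving treatment on this study". Procurement has no washout; 4.1.1 admits "Any patient with biopsy proven pancreatic adenocarcinoma".
- **Group B.** Section 5.2 describes patients "who have failed first line chemotherapy or are intolerant or ineligible to receive standard of care chemotherapy".
- **Group C.** Section 5.2 says "One infusion will occur 4 weeks prior to surgical resection (with an option to infuse up to one week earlier" and puts that infusion after all pre-operative therapy. Section 9.4 says that imaging and the clinical plan are settled before infusion.
- **Scoring.** Section 8.1 defines PR as "At least a 30% decrease in the sum of the longest diameter (LD) of target lesions, taking as reference the baseline sum LD" and counts any new lesion as PD. Section 8.0 adds "All patients who receive multiTAA T cells and continue to be enrolled on the study will be evaluable for response".
- **Reporting.** Section 9.3.2 gives response rates with exact binomial intervals and Kaplan-Meier PFS, by group and for all treated patients. PFS after infusion is the secondary objective (2.3).

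No section orders the scan relative to the last dose of conventional therapy. None says which scan is the baseline when several precede infusion. The provision in 7.3.3 for using additional scans covers only those taken during or after study treatment.

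**The concern.** With no control arm and at most 15 patients per group, the baseline scan is the only thing that separates what happened before the T cells from what happened after them. If that scan is old, two distinct things go wrong.

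1. **Shrinkage credited to T cells (Group B, treated after the scan).** Therapy given between the scan and the washout can shrink the tumour, and 8.1 counts that shrinkage toward PR.
2. **Earlier lesions counted as progression (any Group B patient; Group C less plausibly).** A lesion that appears between the scan and infusion 1 is first seen afterwards and is scored as PD. This depends on the age of the scan, not on therapy in the gap, so a Group B patient who never had chemotherapy is exposed too.

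At stake is how the response rate and PFS curve are read. Once infusion 1 has been given without a recent scan, the two periods of change cannot be separated. Group A is outside this point: 4.3.10 does not apply to it, and its chemotherapy continues by design.

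**Working it through.** The plan states no figure on this point, so there is none to reproduce.

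**Inputs from the documents.** Scan window 8 weeks (7.4); washout 1 week (4.3.10); PR at a 30% fall from baseline, and PD on any new lesion (8.1); follow-up scans every 2-3 months (7.3.3, 8.0); Group C surgery 4-5 weeks after infusion 1 (5.2); at most 15 per group and 45 in all (9.1).

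**Assumed.** All shrinkage values and patient counts below; the documents give none.

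**Step 1: therapy that can fall in the gap.** 8 − 1 = 7 weeks at most. The text permits this and does not require it.

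**Step 2: effect on PR in Group B.** If the sum of diameters has already fallen by a fraction s at infusion 1, the further fall that reaches 70% of baseline is 1 − 0.70/(1 − s).

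| Fall before infusion 1 (assumed) | Further fall needed for PR |
|---|---|
| 0% | 30% |
| 10% | 1 − 0.70/0.90 = 22.2% |
| 15% | 1 − 0.70/0.85 = 17.6% |
| 20% | 1 − 0.70/0.80 = 12.5% |
| 25% | 1 − 0.70/0.75 = 6.7% |

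With 0, 1 or 2 such PRs in 15 and no others, the reported rate and exact 95% interval are:
- 0/15 = 0% (0 to 21.8%)
- 1/15 = 6.7% (0.2 to 31.9%)
- 2/15 = 13.3% (1.7 to 40.5%)

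**Step 3: shrinkage in Group C.** The first follow-up scan falls at 2-3 months, about 8.7 to 13.0 weeks. Resection at 4-5 weeks comes first, so the shrinkage route essentially does not apply. Only the new-lesion route remains.

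**Step 4: effect on PFS.** With no censoring before the first follow-up scan, the Kaplan-Meier estimate there is the proportion event-free. One patient moved from event-free to PD lowers it by 1/15 = 6.7 points in a group, or 1/45 = 2.2 points overall. For example, 10/15 = 66.7% (38.4 to 88.2%) becomes 9/15 = 60.0% (32.3 to 83.7%) with one such patient, or 8/15 = 53.3% (26.6 to 78.7%) with two. These shifts are ceilings: they occur only if the patient would otherwise have been progression-free at that scan.

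**Step 5: size-based PD is not relied on.** Section 8.1 takes the lowest sum from the start of treatment as its reference, which can be read as leaving out the pre-infusion scan. Neither route above depends on that reading.

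**The case against.** The best case on the other side has five parts.

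- **Group B shrinkage is a narrow route.** Eligibility in 4.3.1 is progression after first-line chemotherapy or ineligibility for standard chemotherapy. After a scan showing failure, shrinkage needs some further effective treatment before infusion. Patients intolerant of chemotherapy, who might be scanned, dosed again and then stopped, appear in 5.2 but not in 4.3.1. This stands as a limit on frequency. It does not close the route: second-line therapy or radiotherapy is not excluded, and cells can be made while treatment continues, with blood drawn over up to two months (5.1).
- **Group C would be restaged anyway.** Sections 5.2 and 9.4 make this likely, though neither requires a scan after neoadjuvant therapy. A new metastasis on a fresh scan might also have kept the patient out of Group C, so the 10/15 to 9/15 example describes that case poorly. Group C PFS already reflects surgery and standard care. All this stands, and Group C is the weaker case.
- **Therapy in the gap does not produce new lesions.** A reader might infer that the 7 weeks of treatment drive both errors. They do not: effective therapy would, if anything, make new lesions less likely. Only the age of the scan matters there.
- **A reader might infer that response is inflated, or that PFS is biased one way.** The documents do not support either as a finding. Earlier shrinkage would raise response, earlier lesions would shorten PFS, and no frequency is given for either.
- **The outcomes are descriptive.** Response is tertiary and PFS secondary in a pilot, no decision rule uses them, imaging deliberately follows standard care, and the intervals for 0, 1 and 2 responses in 15 overlap heavily. This limits the severity. It does not justify leaving the baseline undefined when a timing rule is cheap.

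**Conclusion.** The concern holds as a gap in a timing rule, worth correcting but not critical. The text permits a baseline scan 8 weeks old with up to 7 weeks of conventional therapy after it. Section 8.1 would then score change from before infusion 1 as if it followed the T cells.

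For Group B response, each misattributed PR adds 6.7 points to the rate in a group of 15. For PFS, each lesion that predates infusion 1 lowers the first-scan estimate by at most 6.7 points in a group and 2.2 points overall. These sizes rest on full groups of 15, no censoring before the first follow-up scan, and assumed patient counts. Group B carries most of the concern.

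It would go too far to say that the trial's response rate or PFS will be wrong, or wrong in a known direction. The primary safety and feasibility assessments and the sample size are untouched.

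**What to change.** In 7.3.3 and the 7.4 footnote, for Groups B and C:

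1. Time the already required pre-infusion scan after the last dose of conventional therapy and, where scheduling allows, within about 4 weeks of infusion 1. The exact limit is the sponsor's choice.
2. Name the latest pre-infusion scan as the 8.1 baseline.
3. Flag every patient whose baseline scan predates the last dose or is older than the limit. The second condition is needed to catch untreated Group B patients with an old scan.
4. List scan and last-dose dates, and report the 9.3.2 response rate and PFS with and without flagged patients.

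Score flagged patients by 8.1 as usual. Refusing to credit their PRs while keeping them in the denominator would count possible true responders as non-responders and so replace one bias with another. No extra research scan should be mandated.

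**Cost.** Some scans must be rescheduled, and in Group C this has to fit the 4-5 week interval to surgery. The sensitivity summary is slightly less precise: with zero responses, the upper 95% limit moves from 21.8% (0/15) to 23.2% (0/14) or 24.7% (0/13). Imaging reports, pre-study data and concomitant medication are already recorded (11.0, 12.2).

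**What remains.** A lesion can still appear between a recent scan and infusion, and delayed shrinkage after radiotherapy can still be credited to the T cells.
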